#### **6.4.2 Follow-up of unresolved adverse events**

Any AEs that remain unresolved at the patient's last study visit will be followed up by the Investigator for as long as medically indicated, but without further recording in the eCRF. It is acknowledged that the Company may request additional information after the completion of the study.

#### **6.4.3 Variables**

The following variables will be collected for each AE:

- AE (verbatim)
- The date when the AE started and stopped
- Intensity

Adverse Event intensity will be assessed according to the following categories:

- mild (awareness of sign or symptom, but easily tolerated)
- moderate (discomfort sufficient to cause interference with normal activities)
- severe (incapacitating, with inability to perform normal activities)
- Whether the AE is serious or not
- Investigator causality assessment /relationship to the study drug (yes or no)
- Action(s) taken with regard to the study drug
- AE caused the patient's withdrawal from study (yes or no)
- Outcome.

In addition, the following variables will be collected for SAEs:

- Date AE met criteria for serious AE
- Date Investigator became aware of SAE

- Reason for assessing the AE as serious
- For hospitalizations:
  - Date of hospitalization
  - Date of discharge
- For AEs with a fatal outcome:
  - Date of death
  - Probable cause of death
  - Autopsy performed and finding(s)
- Causality assessment in relation to study procedure(s)
- Causality assessment in relation to other medication
- Description of SAE.

Note: It is important to distinguish between serious and severe AEs. Severity is a measure of intensity whereas seriousness is defined by the criteria outlined in [Section 6.2](#). An AE of severe intensity would not necessarily qualify as serious. For example, nausea that persists for several hours may be considered severe, but not a SAE unless it meets the criteria provided in [Section 6.2](#). On the other hand, a stroke that results in only a limited degree of disability may be considered a mild stroke but would be a SAE if it satisfies the criteria provided in [Section 6.2](#).

#### **6.4.4 Causality collection**

The Investigator will assess causal relationship between the study drug and each AE, and answer ‘yes’ or ‘no’ to the question ‘Do you consider that there is a reasonable possibility that the event may have been caused by the investigational product?’

For SAEs, causal relationship will also be assessed for other medication and study procedures. Note that for SAEs that could be associated with any study procedure the causal relationship is implied as ‘yes’.

A guide to the interpretation of the causality question is found in [Appendix A](#) (Additional Safety Information).

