## 2.3 Safety Objectives

Safety Objective #1: Lokelma-Induced Hypokalemia	Safety Outcome Measure:
To evaluate whether the use of oral sodium zirconium cyclosilicate (Lokelma ® ) during periods when patients are receiving a 3.0 K + /2.5 Ca ++ dialysate bath is associated with hypokalemic events defined as K + <3.5 mEq/L.	➤ Total number of hypokalemic events defined as Piccolo POCT or laboratory-measured K + of < 3.5 mEq/L.
Safety Objective #2: Incidence of Dialysis-related Hypokalemia, Hypomagnesemia, Hypophosphatemia, or Low Calcium	Safety Outcome Measure:
To determine the levels of K + , Mg ++ , calcium and PO 4 during dialysis (measured promptly prior to the termination of dialysis) during experimental treatment [2] compared to standard treatment [3]. Note: Each electrolyte is its own "safety" objective independently.	➤ Number of events (measured promptly prior to the termination of dialysis) where a Piccolo POCT measurement of K + is < 3.5 mEq/L OR Ca ++ is < 7.0 mEq/L, OR Mg ++ is < 2.0 mg/dl, OR a PO 4 level is <3.0 mEq/L. All episodes where a specific electrolyte falls below the above listed threshold will be considered an "event" for that electrolyte. The total number of "events" will be recorded during the 8-week Treatment Phase-1 and the 8-week Treatment Phase-2 cross-over periods.
Safety Objective #3: Adverse Experiences	Safety Outcome Measure:
To evaluate the safety and tolerability of the experimental treatment [2] compared to standard treatment [3] based on the frequency of reported adverse experiences.	➤ Frequencies of AEs, SAEs, and withdrawals due to AEs, with focus on treatment-related events.

Abbreviations: AE=adverse event; CSCA=clinically significant cardiac arrhythmia; SAE=serious adverse event

[2] Experimental treatment (8 weeks): hemodialysis using 3.0K+/2.5 Ca++ dialysate bath, with sodium zirconium cyclosilicate (Lokelma®) supplementation on off-treatment days

[3] Standard treatment (8 weeks): hemodialysis using 2.0K+/2.5 Ca++ dialysate bath, without sodium zirconium cyclosilicate (Lokelma®) supplementation

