#### **6.4.6 Adverse events based on examinations and tests**

The results from protocol-mandated laboratory tests and vital signs measurements will be summarized in the clinical study report. Deterioration from baseline in protocol-mandated

laboratory values or vital signs should therefore only be reported as AEs if they fulfil any of the SAE criteria or are the reason for discontinuation of study treatment.

If deterioration in a laboratory value/vital sign is associated with clinical signs and symptoms, the sign or symptom will be reported as an AE and the associated laboratory result/vital sign will be considered as additional information. Wherever possible the reporting Investigator should use the clinical, rather than the laboratory term (e.g., anaemia versus low hemoglobin value). In the absence of clinical signs or symptoms, clinically relevant deteriorations in non-mandated parameters should be reported as AE(s).

Any new or worsened (compared to baseline) clinically relevant abnormal physical examination findings should be reported as an AE.

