## 7. INVESTIGATIONAL PRODUCT AND OTHER TREATMENTS

### 7.1 Identity of Investigational Product(s)

The investigational product (IP) in this study is sodium zirconium cyclosilicate (Lokelma®), a potassium binder product for oral administration. It is indicated for the treatment of hyperkalemia in adults (*Lokelma United States Prescribing Information [USPI], 19th October 2021*).

Lokelma, powder for oral suspension will be supplied in 5.0 gram packets to study participants.

Investigational product	Dosage form and strength
sodium zirconium cyclosilicate (Lokelma ® )	For oral suspension: 5 g of white to grey powder in a foil-lined packet.

Note: In this protocol, the terms investigational product, IP, and study drug are used interchangeably.

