#### **8.4.8 Safety Endpoint #3: Adverse Experiences**

The frequencies of AEs, SAEs, and withdrawals due to AEs will be summarized, with focus on treatment-related events.

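### For non-serious adverse events causality is asked only about Lokelma, so the treatment-related part of safety objective #3 is not a like-for-like comparison of the two regimens

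*Protocol*

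**What the plan says.** Section 2.3 states safety objective #3 as "To evaluate the safety and tolerability of the experimental treatment [2] compared to standard treatment [3] based on the frequency of reported adverse experiences". The two footnoted treatments are the 3.0 K bath with Lokelma and the 2.0 K bath without it. The outcome measure is "Frequencies of AEs, SAEs, and withdrawals due to AEs, with focus on treatment-related events", and Section 8.4.8 repeats it: "The frequencies of AEs, SAEs, and withdrawals due to AEs will be summarized, with focus on treatment-related events".

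Among the variables collected for every AE, the causality item in Section 6.4.3 reads "Investigator causality assessment /relationship to the study drug (yes or no" (a yes/no field). Section 6.4.4 gives the wording of the question: "Do you consider that there is a reasonable possibility that the event may have been caused by the investigational product". Section 7.1 fixes what that covers: "The investigational product (IP) in this study is sodium zirconium cyclosilicate", and "In this protocol, the terms investigational product, IP, and study drug are used interchangeably". The dialysate is not part of the investigational product.

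SAEs are treated differently. Sections 6.4.3 and 6.4.4 add relationship to other medication and to study procedures. Section 6.2 describes SAE causality more broadly, as covering all study treatment as well as procedures.

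Section 8.5.6 summarises AEs, SAEs, AEs leading to withdrawal and AEs leading to death by treatment group and period without reference to causality. As an additional table it presents AEs by relationship to Lokelma.

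**The concern.** The comparison in objective #3 is between regimens, and the bath differs in both of them: it is half of the experimental treatment and all of the standard one. The causality item covers only the other half. An investigator who thinks that a cramp or a hypotensive episode came from the bath has to answer no in either period. An investigator who thinks that constipation came from Lokelma can answer yes, and in practice almost only for events on or shortly after Lokelma.

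The emphasised part of the objective therefore sets Lokelma attributions on one side against a period with almost nothing to attribute on the other. Effects of the bath are what the trial is about: Section 1.2 proposes that the 2.0 K bath contributes to arrhythmia, and Section 1.1.1 accepts inter-dialytic hyperkalemia as a legitimate worry with a higher-potassium bath. A reader of the treatment-related table could take it as evidence on the regimens when it is evidence on one component of one regimen.

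**Working it through.** The protocol gives no figure on this point to reproduce. The check is to trace which attributions can be recorded, for which patients and in which period.

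**Inputs**
- Allocation 1:1, 44 patients per sequence, 88 in total (Section 8.2). The sequences are named here by order of treatment.
- Schedule (Table 1): crossover on day 71, second accommodation period days 71 to 84, second treatment phase days 85 to 140.
- Treatment-emergent window on Lokelma: from first dose to 14 days after last dose (Section 8.5.6).
- Causality fields: study drug for all AEs; study procedures and other medication for SAEs only (Sections 6.4.3 and 6.4.4).
- Appendix A asks the investigator to consider whether the patient actually received the suspect drug and whether another cause explains the event.

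**Step 1: 2.0 K taken first (44 patients).** No study Lokelma has been given. Under the Appendix A exposure factor the answer is no, so related non-serious AEs are zero in practice.

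**Step 2: 2.0 K taken second (44 patients).** With the last dose on day 70, the window ends on day 70 + 14 = 84. It covers days 71 to 84, which are 14 of the 70 days (71 to 140) on the 2.0 K bath, or 14/70 = 20%. A yes is plausible there. In the remaining 70 − 14 = 56 days it is not expected, though nothing forbids it.

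**Step 3: which attributions can be recorded as related**

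| Event and suspected cause | 2.0 K first | 2.0 K second | 3.0 K plus Lokelma |
|---|---|---|---|
| Non-serious, Lokelma | No in practice | Possible, mainly days 71–84 | Possible |
| Non-serious, dialysate | No field | No field | No field |
| Serious, dialysate | Depends on reading | Depends on reading | Depends on reading |

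**Step 4: the SAE row.** Under Section 6.2 the bath is covered if it counts as study treatment. The synopsis, under Duration of treatment, uses that term for both baths, which supports this reading. But the fields listed in Sections 6.4.3 and 6.4.4 are study drug, study procedures and other medication, and nowhere is the dialysate called a study procedure. The two descriptions have to be reconciled.

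**Step 5: which summaries depend on the item.** The counts of AEs, SAEs, withdrawals and deaths by treatment and period do not. The relationship-to-Lokelma table and any treatment-related summary do.

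**The case against.** The strongest reply is that the objective does not rest on causality. It is framed on the frequency of reported adverse experiences, its measure is all AEs, SAEs and withdrawals, and treatment-related events are an emphasis within that. The relatedness table is an addition and is labelled as relationship to Lokelma. The expected effects of changing the bath are also measured in both periods without any investigator attribution: electrolyte threshold events, potassium outside 4.0 to 5.5 mEq/L, loop-recorder arrhythmias with blinded adjudication of atrial fibrillation, intradialytic hypotension and cramping. Finally, the trial is open-label, so attribution to a known bath is prone to bias, and the all-cause comparison is the better one.

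All of this stands, and it limits the point. It does not remove it, because the protocol itself singles out treatment-related events in a comparison of regimens and then collects an attribution that covers only part of one. Nor can the matter be left to the analysis plan. A plan can define a table, but it cannot recover a judgement that was never asked for, and Section 6.4.3 lists the variables to be collected.

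A reader might go further in four ways that the documents do not support:
- *Objective #3 cannot be answered.* The all-cause summaries in Section 8.5.6 answer its main part.
- *Related events in the standard period are zero by construction.* That holds in practice for patients who start on 2.0 K. For the others the 14-day tail leaves room for a yes.
- *The ratio of related events is infinite.* No ratio is planned; Section 8.5.6 reports safety descriptively in general.
- *Section 6.4.6 adds a second asymmetry*, since laboratory changes "should therefore only be reported as AEs if they fulfil any of the SAE criteria or are the reason for discontinuation of study treatment". The synopsis uses study treatment for both regimens, and the seriousness criteria apply equally in both periods.

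**Conclusion.** The point holds for the treatment-related component of objective #3 and for non-serious AEs. That component is not like-for-like: related events are zero in practice for the 44 planned patients who take 2.0 K first, and expected to be near zero for the other 44 apart from about 14 of their 70 days on 2.0 K. Non-serious AEs attributed to either bath cannot be recorded as related in any period. For SAEs coverage of the bath is unclear rather than absent. No event count can be put on this, because the protocol gives no expected AE rates.

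The conclusion assumes that investigators follow Appendix A, that Lokelma is last taken on day 70 as scheduled, and that the collected items are those listed in Section 6.4.3. It also assumes that non-serious AEs are collected in a first 2.0 K period. Section 6.4.1 starts collection at the first Lokelma dose, which conflicts with the 2.0 K treatment-emergent definition in Section 8.5.6. That is a separate matter, and it needs settling for the all-cause comparison as well.

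This is a worthwhile, inexpensive improvement to the plan, not a flaw that invalidates the safety assessment.

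**What to change.** 1. In Sections 6.4.3 and 6.4.4, add a yes/no item for every AE in both periods on relationship to the assigned dialysate (2.0 K or 3.0 K), alongside the existing Lokelma item.
2. In Sections 8.4.8 and 8.5.6, define treatment-related as related to the assigned regimen, meaning bath or Lokelma. Report relationship to Lokelma alone only as a description of the 3.0 K period.
3. In the same sections, state that the between-treatment comparison rests mainly on all-cause treatment-emergent AEs, because attribution is unblinded.
4. Reconcile Section 6.2 with Sections 6.4.3 and 6.4.4 on whether SAE causality covers the dialysate.

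The cost is one extra eCRF field, a few sentences, and one more judgement per AE for the investigator. The new attribution is open-label and should be read with that in mind, which is the reason for item 3.

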#### **6.4.5 Adverse events based on signs and symptoms**

All AEs spontaneously reported by the subject or reported in response to the open question from study personnel: ‘*Have you had any health problems since your previous study visit?*’ or revealed by observation will be collected and recorded in the eCRF. It is preferred that AE are recorded as diagnoses (when possible) rather than a list of signs and symptoms. However, if there are other signs or symptoms that are not generally part of the diagnosis, the diagnosis and each sign or symptom should be recorded separately.

#### **6.4.6 Adverse events based on examinations and tests**

The results from protocol-mandated laboratory tests and vital signs measurements will be summarized in the clinical study report. Deterioration from baseline in protocol-mandated

laboratory values or vital signs should therefore only be reported as AEs if they fulfil any of the SAE criteria or are the reason for discontinuation of study treatment.

If deterioration in a laboratory value/vital sign is associated with clinical signs and symptoms, the sign or symptom will be reported as an AE and the associated laboratory result/vital sign will be considered as additional information. Wherever possible the reporting Investigator should use the clinical, rather than the laboratory term (e.g., anaemia versus low hemoglobin value). In the absence of clinical signs or symptoms, clinically relevant deteriorations in non-mandated parameters should be reported as AE(s).

Any new or worsened (compared to baseline) clinically relevant abnormal physical examination findings should be reported as an AE.

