### **3.9 Discontinuation of Investigational Product**

Patients may be discontinued from investigational product (IP) in the following situations:

- Patient decision. The participant is at any time free to discontinue treatment, without prejudice to further treatment;
- Incorrectly randomized participant where violation of the inclusion/exclusion criteria would put the participant at undue risk;
- Adverse event for which the investigator judges continued treatment may put the participant at undue risk;
- Pregnancy;
- Development of any of the following study-specific criteria for discontinuation:
  - Permanent atrial fibrillation, as determined by echocardiogram or cardiology assessment;

- Requiring for permanent placement of a cardiac pacemaker or AICD;
  - Refractory hyperkalemia ( $K^+ > 6.5$  mEq/L) while on 15 grams 4 days per week of Lokelma;
  - Hypokalemic event (defined as pre-dialysis  $K^+$  level of  $< 3.5$  mEq/L): Patients experiencing a minimum of two (2) hypokalemic events while taking Lokelma will have their Lokelma adjusted or discontinued at the discretion of the site PI;
  - Renal transplant.
- Severe non-compliance with the study protocol.

Note: patients wishing to remain in the study on treatment despite developing an adverse event may do so at the site PI's discretion, unless they remain hyperkalemic with  $K^+ > 6.5$  mEq/L after a long inter-dialytic interval (LIDI) for two (2) consecutive weeks.

Regardless of the reason for discontinuation, all reasons for discontinuation of study treatment must be documented in the electronic case report form (eCRF).

If the patient is discontinued from investigational product, the scheduled study visits, data collection and procedures should continue according to the study protocol until study completion, unless the patient withdraws consent for any further study procedures and follow-up. The approach taken should be documented in the eCRF.

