#### **8.5.6 Safety Analyses**

Lokelma-induced hypokalemia will be evaluated based on the total number of hypokalemic events defined as PiccoloPOCT or laboratory-measured K+ of < 3.5 mEq/L.

The incidence of dialysis-related hypokalemia, hypomagnesemia, hypophosphatemia, and low calcium will be evaluated based on the number of events promptly prior to the termination of dialysis where a PiccoloPOCT measurement of K+ is < 2.0 mEq/L OR Ca++ is < 7.0 mEq/L, OR Mg++ is < 2.0 mg/dl, OR a PO4 level is < 3.0 mEq/L. All episodes where a specific electrolyte falls below the above listed threshold will be considered an “event” for that electrolyte. The total number of “events” will be recorded during the 8-week Treatment Phase-1 and the 8-week Treatment Phase-2 cross-over periods and compared between the treatments.

Safety will also be assessed in terms of the frequency of AEs, SAEs, and withdrawals due to AEs, with focus on treatment-related events. Appropriate summaries of these data will be presented by treatment group and/or study period.

Adverse events will be coded using the Medical Dictionary for Regulatory Activities (MedDRA) system organ class (SOC) and preferred term (PT). A treatment-emergent AE

(TEAE) is defined as an AE with the start date on or after the first dose date and up to (and including) 14 days after the last dose date in each of study periods when patients received 3K Bath with Lokelma. However, when patients received 2K Bath without Lokelma, A treatment-emergent AE (TEAE) is defined as an AE with the start date on or after the first visit date and up to (and including) 14 days after the last visit date in each of study periods. Only TEAEs will be included in table summaries.

The number and percentage of participants experiencing AEs, SAEs, AEs that led to withdrawal, AEs that led to death, and the number of such events, will be summarised by SOC, PT, and treatment group and study period. The number and percentage of participants experiencing AEs will further be summarised by intensity and will be presented with the number of events at each level of intensity.

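### Section 6.4.6 makes stopping *study treatment*, a term the protocol does not define, a condition for recording non-serious laboratory AEs; almost all written stopping rules concern Lokelma, so these AEs are recorded more readily on 3.0 K + Lokelma than on the 2.0 K bath

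*Protocol*

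**What the plan says.** **The recording rule.** Section 6.4.6 says that a deterioration from baseline in a protocol-mandated laboratory value or vital sign "should therefore only be reported as AEs if they fulfil any of the SAE criteria or are the reason for discontinuation of study treatment". If symptoms accompany the value, "the sign or symptom will be reported as an AE and the associated laboratory result/vital sign will be considered as additional information".

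**The stopping rules.** Section 3.9 opens with "Patients may be discontinued from investigational product (IP) in the following situations". Its hyperkalemia criterion applies "while on 15 grams 4 days per week of Lokelma". Under its hypokalemia criterion, patients with at least two "hypokalemic events while taking Lokelma will have their Lokelma adjusted or discontinued at the discretion of the site PI". Section 7.1 states that "the terms investigational product, IP, and study drug are used interchangeably"; *study treatment* is not in that list.

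**The comparison.** Safety objective #3 in section 2.3 is "To evaluate the safety and tolerability of the experimental treatment [2] compared to standard treatment [3] based on the frequency of reported adverse experiences". Section 8.5.6 summarises "The number and percentage of participants experiencing AEs, SAEs, AEs that led to withdrawal, AEs that led to death, and the number of such events" by system organ class, preferred term, treatment group and study period.

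**The concern.** An AE comparison between two treatments is fair only if the same finding has the same chance of becoming an AE record on each. Here, a non-serious laboratory value without symptoms becomes an AE because of what was done to treatment, not because of the value. If the written reasons for stopping belong almost entirely to one regimen, the AE table for that regimen collects events that the other table does not.

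This matters because section 1.2 rests the trial on the premise that dialysis with the 2.0 K bath contributes to low potassium and arrhythmia. An AE table that picks up asymptomatic potassium abnormalities more readily on the experimental regimen could show an excess there even when low values are equally common, or more common, on the standard bath.

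**Working it through.** No arithmetic applies: the protocol gives no figure on this point. The check sets the passages side by side.

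**1. What *study treatment* covers.** Section 7.1 equates only investigational product, IP and study drug, all meaning Lokelma. The synopsis, under duration of treatment, has patients begin study treatment on either bath and counts 20 weeks of it in total, so there the term includes the 2.0 K bath. Section 3.9 uses the term when it asks for stopping reasons in the eCRF, within the section on stopping Lokelma. The wording supports both readings.

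**2. Laboratory- or ECG-triggered stopping rules.**

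| Section | Trigger | What it is tied to |
|---|---|---|
| 3.9 | K+ above 6.5 mEq/L despite the top dose | Lokelma |
| 3.9 (also 5.3.1 and 6.9) | at least two pre-dialysis K+ below 3.5 mEq/L | Lokelma |
| 7.2.1 | potassium target not reached after the top dose | Lokelma |
| 3.11 | QTc limits | study drug, i.e. Lokelma |
| 3.9, note | K+ above 6.5 mEq/L after the long interval for two consecutive weeks | no regimen named |

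Four rules are tied to Lokelma, one names no regimen, and none is specific to the 2.0 K bath. The QTc rule concerns an ECG finding rather than a laboratory value; it is listed because it shows which treatment is stopped. For low potassium, calcium, phosphate or magnesium on the 2.0 K bath there is no written stopping rule.

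**3. The same finding in each period.** Take two asymptomatic, non-serious pre-dialysis K+ values below 3.5 mEq/L.

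- *On 3.0 K with Lokelma:* under sections 3.9 and 5.3.1 the drug is either adjusted, and 6.4.6 creates no AE, or discontinued, and it creates one. Under section 6.9 the drug is permanently discontinued, which creates one. Whether an AE exists depends on which passage the site follows and on the site's discretion.
- *On the 2.0 K bath:* no passage prescribes stopping. An AE arises only if the investigator stops the bath for that reason and reads *study treatment* as including it.

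The chance of a record differs between periods for the same values.

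**4. Where the record goes.** Section 8.5.6 tabulates it by treatment group, and objective #3 compares the treatments on AE frequency. Section 8.5.6 also presents AEs leading to discontinuation of Lokelma by organ class and preferred term, but plans no between-treatment AE summary without them.

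**5. What is captured elsewhere.** Sections 5.2.1, 8.4.3, 8.4.7 and 8.5.6 count or compare electrolyte events across both treatments from scheduled samples, and 8.5.6 adds shift tables. None of these changes the AE table.

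**The case against.** The strongest reply has four parts.

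- **Section 6.4.6 does not say Lokelma.** A reader might infer that these AEs cannot be recorded on the 2.0 K bath at all. The documents do not support that: on the synopsis's usage of *study treatment*, a value that led to stopping the 2.0 K bath is reportable. The potassium note in 3.9 could also apply on either regimen, although it concerns high potassium only. What stands is unequal likelihood, not impossibility.
- **Stopping Lokelma is not automatic.** A reader might infer that two low potassium values always become an AE on the experimental regimen. Sections 3.9 and 5.3.1 allow adjustment, which creates none. This weakens any claim of a fixed asymmetry, but makes the count depend on site choice.
- **Electrolyte harms are compared directly.** This is largely right and limits the damage: symptomatic and serious events fall under 6.4.6 whichever bath is used, and the laboratory endpoints cover both periods. It would be wrong to call the whole comparison of electrolyte harms one-sided. Those endpoints are not clean themselves, however. The end-of-dialysis potassium threshold is 3.5 mEq/L in 2.3 but 2.0 mEq/L in 8.4.7 and 8.5.6, and 8.4.6 frames hypokalemia below 3.5 mEq/L for the 3.0 K period while 5.2.1 compares it between treatments.
- **Section 6.4.1 is a wider gate.** It starts non-serious AE collection at the first Lokelma dose. For the sequence that begins on the 2.0 K bath, this leaves Days 1 to 70 without such collection, against the TEAE window in 8.5.6. That is a separate problem, and correcting it would leave 6.4.6 uneven.

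**Conclusion.** The point holds in a limited form. Section 6.4.6 ties the recording of non-serious, asymptomatic laboratory AEs to an undefined term, and the written laboratory reasons for stopping lie almost entirely on the Lokelma side. Following the text gives differential ascertainment in a table that the protocol uses to compare treatments. The likely direction is more recorded events on 3.0 K with Lokelma.

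The effect is confined to descriptive AE tables. It does not touch the primary endpoint, SAEs, symptomatic events or the laboratory endpoints.

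Its size cannot be derived, because the protocol gives no rate of stopping Lokelma for laboratory values. A reader might assume that 5% to 10% of 88 patients stop for potassium (0.05 × 88 = 4.4; 0.10 × 88 = 8.8) and infer about 4 to 9 patients against 0. That assumes the stopping rate, requires every stop to be non-serious and asymptomatic, and requires reading *study treatment* as Lokelma alone. A contrast of 100% missed against 0% missed is no better, since it sets all standard-period laboratory events against only those that stopped Lokelma.

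**What to change.** - **Section 6.4.6:** define *study treatment*, stating whether it includes the 2.0 K bath. Keep recording and reporting these AEs and any withdrawals, because section 2.3 makes withdrawals due to AEs part of the safety outcome. Add a flag for AEs recorded only because a mandated laboratory value led to stopping Lokelma.
- **Section 8.5.6:** keep the planned tables and add one between-treatment AE summary that excludes the flagged events. State that the comparison of electrolyte harms rests on the laboratory endpoints measured in both periods, and reconcile their thresholds and scope across 2.3, 5.2.1, 8.4.6, 8.4.7 and 8.5.6.
- **Sections 3.9 and 5.3.1 against 6.9:** reconcile what follows two hypokalemic events. Which rule is right is a clinical decision; the statistical need is a single statement, since it determines when this route creates an AE.
- **Separately:** reconcile the start of AE collection in 6.4.1 with the TEAE window in 8.5.6.

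For the 6.4.6 problem itself, the cost is one definition, one flag and one extra table. No new samples are needed, because both baths already have weekly measurements.
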